4.2.2.2 Pharmacokinetics Endpoints

PK endpoints to be evaluated include (but are not limited to):

- plasma concentrations of EQ101 [REDACTED] and [REDACTED]
- incidence of antidrug antibody (ADA) [REDACTED]

[REDACTED] [REDACTED]

[REDACTED]

[figure not shown]
[REDACTED]

[REDACTED]

[REDACTED]

[REDACTED]

[REDACTED]

6 STATISTICAL CONSIDERATIONS

6.1 Standard Operating Procedures and Software

Data will be handled and processed per the sponsor representative's [REDACTED] Standard Operating Procedures (SOPs), which are written based on the principles of Good Clinical Practice (GCP).

All data conversions and statistical analyses will be performed using SAS® Version 9.4 or higher (SAS Institute, Cary, North Carolina, USA) with program code prepared specifically for the study by qualified Avance statisticians and SAS® programmers.

6.2 General Considerations

All data collected during the study (data originating from the electronic Case Report Forms (eCRFs) or electronic transfers will be presented in the data listings. Event-based listings will be sorted by subject identifier and event start date/time (i.e., Adverse Event (AE) start date/time). Assessment-based listings will be sorted by parameter name (alphabetically unless specifically stated otherwise), subject identifier, visit, assessment date and time (if applicable).

Unless otherwise stated, the following methods will be applied:

- Continuous variables: Descriptive statistics will include the number of non-missing values (n), arithmetic mean, standard deviation, median, minimum, and maximum values.

The minimum and maximum values will be displayed to the same decimal precision as the source data, the arithmetic mean and median values will be displayed to one more decimal than the source data, and the standard deviation (SD) values will be displayed to two more decimals than the source data for the specific variable.

The appropriate precision for derived variables will be determined based on the precision of the data on which the derivations are based, and statistics will be presented in accordance with the abovementioned rules.

- Categorical variables: Descriptive statistics will include frequencies and percentages per category. The denominator in all percentage calculations will be the number of subjects in the relevant analysis population, unless specifically stated otherwise. Percentages will be rounded to one decimal place and will not be displayed for zero frequencies.
- Repeat/unscheduled assessments: When values collected at scheduled study visits/time points is missing, repeat or unscheduled assessments closest to the scheduled visit date within the visit window defined in Table 1 and Table 2 will be used for the visit to calculate summary statistics in summary tables with visits as defined in section 6.6. All collected data will be included in the data listings. If an unscheduled visit was intended to replace the missing assessment for a scheduled visit this should be documented clearly before values are used as a scheduled visit assessment.
- Assessment windows: All assessments will be included in the data listings including additional safety labs collected and the protocol specified visit windows will not be applied to exclude assessments that were not performed on the protocol specified visit days. Visit information in the CRF will be used in the tables, listings, and figures.
- Result display convention: Results will be centre aligned in all summary tables and listings. subject numbers, visit, and parameter labels and comments may be left aligned

- Conversion of categorical values: In some instances, results may be with less than or greater than signs (i.e., < 9). The original source data captured will be displayed in the data listings (i.e., <9), while values may be converted to numbers which are half of the threshold value for summary table purposes. As an example, a value of < 9 may be converted to 4.5 before calculating summary statistics. In listings, the original value (i.e., <9) is displayed instead of imputed values.
- Date and time display conventions: The following display conventions will be applied in all outputs where dates and/or times are displayed:
 - Date only: YYYY-MM-DD
 - Date and time: YYYY-MM-DD/HH:MM

If only partial information is available, unknown components of the date or time will be presented as UN (Unknown), for example “2022-UN-UN” or “UN:UN” for time.

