6.3 Key Definitions

The following definitions will be used:

- Date of the First Study Treatment Administration: The date of the first study treatment administration is defined as the earliest date on which a study treatment was administered.
- Baseline: The Baseline value is defined as the last available valid, non-missing observation for each subject prior to first study treatment administration on Day 1. If day 1 assessment has time missing, it will be considered as the baseline.
- Change from Baseline: The change from Baseline value at each visit will be calculated for all continuous parameters using the following formula when both values are available:

$$\text{Change from Baseline Value} = \text{Result at specified visit} - \text{Baseline Value}$$

- % Change from Baseline: The % change from baseline value is defined as Change from Baseline divided by Baseline value. Study Day: The study day of an event is defined as the relative day of the event starting with the date of the first study treatment administration (reference date) as Day 1 (there will be no Day 0).

The study day of events occurring before the first study treatment administration will be calculated as:

$$\text{Study Day} = (\text{Date of Event} - \text{Date of First Study Treatment Administration})$$

For events occurring on or after Day 1, study day will be calculated as:

$$\text{Study Day} = (\text{Date of Event} - \text{Date of First Study Treatment Administration}) + 1$$

Study days will only be calculated for events with complete dates and will be undefined for events that are ‘Ongoing’ at the end of the study.

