6.6 Visit Display Conventions

Visit Label for Summary Tables:

The following visit labels will be used in table summary outputs as applicable. Visit window defined in section 6.7 will be applied. :

- Screening
- Baseline
- Day 1 Post-dose
- Week 1
- Week 2
- Week 3
- Week 4
- Week 5
- Week 6
- Week 7
- Week 8
- Week 9
- Week 10
- Week 11
- Week 12
- Week 13
- Week 14
- Week 15
- Week 16
- Week 17
- Week 18
- Week 19
- Week 20
- Week 21
- Week 22

- Week 23
- Week 24
- EOT¹
- Week 28
- EOS²

Visit Label for Data Listings:

For listings, CRF labels will be used.

[REDACTED]

[REDACTED]

[REDACTED]

[figure not shown]
[REDACTED]

[REDACTED]

[REDACTED]

[REDACTED]

[REDACTED]

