7.2 Safety Population (SP)

Consists of all subjects who receive at least one dose of study drug. This analysis population is used for safety and efficacy analysis.

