17 SAFETY

All safety endpoints will be analyzed using the Safety Population.

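### Two general rules in SAP 6.2, followed literally, put wrong or diluted entries in the safety tables: `>` results are halved, and by-visit laboratory and ECG percentages are divided by everyone dosed

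*SAP*

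**What the plan says.** **Results with a sign.** SAP 6.2 (conversion of categorical values) recognises that "results may be with less than or greater than signs" and then offers a single conversion: "values may be converted to numbers which are half of the threshold value for summary table purposes". The only worked example is `<9`, which becomes 4.5. Listings keep the result as reported. The readable text has no separate rule for `>`.

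**Percentages.** SAP 6.2 (categorical variables) states: "The denominator in all percentage calculations will be the number of subjects in the relevant analysis population, unless specifically stated otherwise". For safety, SAP 17 says "All safety endpoints will be analyzed using the Safety Population", and SAP 7.2 defines that population: "Consists of all subjects who receive at least one dose of study drug". SAP 17.2 asks for by-visit normal/abnormal counts and percentages for haematology, chemistry, coagulation and urinalysis, and for low/normal/high shift tables. SAP 17.4 asks for by-visit counts and percentages of the ECG clinical result. Neither section names another denominator or a missing category, so the 6.2 default applies.

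**Continuous data are handled differently.** SAP 6.2 says: "Descriptive statistics will include the number of non-missing values (n), arithmetic mean, standard deviation, median, minimum, and maximum values". Under SAP 6.3, change from baseline "will be calculated for all continuous parameters using the following formula when both values are available". Missing values are therefore visible in the continuous summaries but not in the percentages.

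**The concern.** A value above a limit should not enter a mean as half that limit. For `<x`, x/2 lies inside the range the result allows; for `>x` it lies outside, and it can turn a rise from baseline into a fall.

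The denominator rule counts a dosed subject with no result at a visit as neither normal nor abnormal, yet keeps that subject in the denominator. Both percentages then shrink as attendance falls.

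SAP 4.2.1 lists changes in laboratory results and in ECG parameters among the primary endpoints. The study has a single arm, so these tables are read mainly by comparing one visit with another. If the number assessed differs between visits, the printed percentage can move in the opposite direction to the rate among those assessed. The plan's AE rules impute missing severity and causality to the worst case; here missing results lower the abnormal percentage instead.

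**Working it through.** **Inputs from the documents**

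- Conversion factor 0.5, applied to the threshold (SAP 6.2).
- Percentage denominator: the Safety Population, that is, everyone dosed (SAP 6.2, 7.2, 17).
- About 30 subjects planned (SAP 4.1), used here as 30 dosed.

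**Assumed inputs.** The documents give no dropout rate, abnormality rate or `>` threshold. I assume 0, 1, 3 or 6 subjects without a result, 20% abnormal among those assessed, and a `>90` result with other values at 85.

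**1. Conversion**

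The plan's own example reproduces: 9 × 0.5 = 4.5.

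The same rule applied to `>90` gives 90 × 0.5 = 45, below the limit the result exceeded.

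- Change for a subject going from 85 to `>90`: 45 − 85 = −40 under the rule. The true change is more than 90 − 85 = +5.
- Visit mean with 29 results of 85 and one `>90`: (29 × 85 + 45)/30 = 83.7 under the rule. With `>90` set to 90 it is (29 × 85 + 90)/30 = 85.2. The difference is 45/30 = 1.5.

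**2. Denominator**

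Printed % = (events/assessed) × (assessed/dosed) = events/dosed.

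| No result | Assessed/dosed | Abnormal printed (20% of assessed) | Normal printed (80% of assessed) |
|---|---|---|---|
| 0 | 30/30 | 20.0% | 80.0% |
| 1 | 29/30 | 19.3% | 77.3% |
| 3 | 27/30 | 18.0% | 72.0% |
| 6 | 24/30 | 16.0% | 64.0% |

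Worked case in whole subjects:

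- Baseline: 6 of 30 abnormal = 20.0%.
- Later visit: 24 assessed, 5 abnormal and 19 normal. Among those assessed this is 5/24 = 20.8% and 19/24 = 79.2%.
- Printed under SAP 6.2: 5/30 = 16.7% and 19/30 = 63.3%, which sum to 24/30 = 80.0%.

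The rate among those assessed rises from 20.0% to 20.8%; the table shows a fall from 20.0% to 16.7%.

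**3. What is not affected**

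Mean changes from baseline need both values and are shown with the non-missing n, so the denominator rule does not touch them. AE incidence uses everyone dosed, which is the proper denominator there.

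**The case against.** On conversion, the wording is permissive, the only example is a `<` value, and no readable text names an analyte reported with `>`. This looks like a drafting slip, and the −40 is one subject's value while the planned output is a summary. Setting `>x` to x is also a convention, since x itself is strictly excluded. All of that is fair. But the rule names both signs and offers nothing else for `>`, so a programmer must either enter an impossible value or make an undocumented choice. The threshold is at least the nearest bound.

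On denominators, a fixed population denominator is reproducible and can be overridden, and a by-visit denominator drops subjects who stopped, perhaps because of an abnormality. SAP 6.2 also fills a missing scheduled value with the closest repeat or unscheduled result inside the window, which reduces the gaps. The reversal above needs 6 of 30 missing and hides a small rise. By-visit status tables are also less direct displays of change than the continuous summaries. These points limit the frequency and weight of the problem, but they leave the rule as it is. Missing visits remain foreseeable: Protocol 4.3.1 provides for missed doses and permanent discontinuation. A dosed subject who is replaced under Protocol 4.3.3 stays in the Safety Population.

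Some SAP text is not visible. SAP 6.6 states "Visit window defined in section 6.7 will be applied", but Section 6.7 cannot be read, so how early end-of-treatment and end-of-study results are assigned to visits is unknown. No Section 6.5 heading appears either. An exception there cannot be excluded, but the readable text of 6.2, 17.2 and 17.4 points to none.

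**Conclusion.** The concern holds on the readable text, and it is minor. As written, SAP 6.2 provides an impossible value for `>` results and dilutes every by-visit laboratory, shift and ECG percentage by the factor assessed/dosed. That factor is exact; the counts are assumptions. With 30 dosed and 20% of those assessed abnormal, one missing subject costs 0.7 percentage points (20.0% to 19.3%) and six cost 4.0 (20.0% to 16.0%).

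No hypothesis test or decision rule depends on these tables. Listings keep the original results, counts stand beside the percentages, and the continuous laboratory and ECG summaries show n, so a careful reader can detect both problems. A reader should still not have to recompute percentages that support the primary safety endpoints.

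**What to change.** In SAP 6.2, replace the conversion rule with: results reported as `<x` are set to x/2; results reported as `>x` are set to x.

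In SAP 17.2 and 17.4, add: by-visit percentages use subjects with a non-missing result at that visit as the denominator (for shift tables, a non-missing baseline and visit result); this number is shown and the number missing is reported.

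Leave the AE incidence and efficacy responder denominators as they are.

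The cost is two sentences and minor programming, with no new data. The drawback is a denominator that varies by visit and no longer counts subjects who have stopped; printing the number missing at each visit discloses this.

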6.4 Multiple Comparisons and Multiplicity

No multiplicity adjustment will be carried out for this study.

Adverse Events:

For adverse events with unknown intensity (severity) or unknown relationship to study treatment, these will be imputed as follows:

- If the intensity (severity) of an adverse event is unknown/missing, the intensity will be imputed for the summary of adverse events as being the highest intensity, i.e., “Severe”.
- If the relationship to investigational product of an adverse event is unknown/missing, the relationship will be imputed for the summary of adverse events as being “Related”.

For adverse events, where either the onset time or end time (resolution time) is unknown, AE duration (in days) will be imputed as follows:

- If onset date is unknown

- and it cannot be confirmed that onset was prior to the start of dose administration, then the AE will be classified as treatment-emergent adverse events (TEAE), and AE duration will be shown on the listing as UNKNOWN.
- If onset time is unknown:
 - If the date of onset is known to be same as the date of first dose administration, and it cannot be confirmed that onset was prior to the start of dose administration the AE will be reported as TEAE.

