17.2 Safety Laboratory Assessments

For the haematology, serum chemistry and coagulation, continuous data summary statistics (as described in Section 6.2) and count and percentages of normal and abnormal (defined by a test-specific normal range) will be presented for values, change from baseline at each visit.

In addition, Shift from Baseline at each visit for haematology, serum chemistry and coagulation lab parameters (low, normal, high) will also be presented using counts and percentages in shift tables.

For urinalysis and urine microscopy, continuous data summary statistics (as described in Section 6.2) and count and percentages of normal and abnormal will be presented for values at each visit.

The listings of laboratory parameters (haematology, serum chemistry, coagulation, and urinalysis) will include all the information collected. In addition, the observations that are used as the baseline record (value) for each parameter will be flagged, and the change from baseline values (where applicable) at each post baseline (scheduled and unscheduled) visit will be presented. These listings will be presented sorted by Subject ID and assessment date for the Safety Population, along with age, sex, race, and baseline weight of the subject.

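### Minor: SAP 6.2 halves results reported with either sign, so a result above a limit would be summarised at a value it cannot have

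*SAP*

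**What the plan says.** **Main point.** The conversion bullet in SAP 6.2 opens by noting that "results may be with less than or greater than signs". It then gives one treatment for them: "values may be converted to numbers which are half of the threshold value for summary table purposes". Its illustration is that "a value of < 9 may be converted to 4.5 before calculating summary statistics". The bullet keeps the original signed result in the listings. No visible text gives a different treatment for greater-than results.

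The summaries that would use the converted numbers are set out in the same section: "Descriptive statistics will include the number of non-missing values (n), arithmetic mean, standard deviation, median, minimum, and maximum values". SAP 17.2 applies these statistics to haematology, serum chemistry and coagulation (values and changes from baseline) and to urinalysis (values). Protocol 2.2.1 and SAP 4.2.1 list changes in laboratory results among the primary endpoints.

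**Secondary wording, baseline.** SAP 6.3 defines baseline as the "last available valid, non-missing observation for each subject prior to first study treatment administration on Day 1". It then adds: "If day 1 assessment has time missing, it will be considered as the baseline". Protocol 6.3.7 and 6.3.8 schedule vital signs and an ECG both before and about 30 minutes after dosing on Day 1.

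**Secondary wording, adverse events.** The imputation text printed under SAP 6.4 assigns a missing severity to the highest intensity and names that category as severe. Protocol 6.3.2.1 grades events on the five-point CTCAE scale, and the SAP 17.1 tables run from Grade 1 to Grade 5.

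**The concern.** Half the threshold lies inside the possible range of a less-than result. It lies outside the possible range of a greater-than result. The rule therefore takes a value known to be high and enters it as a low one.

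The extremes suffer most. The highest result at a visit could be missing from the maximum and appear as the minimum. A subject whose value rose could be shown as having fallen. In a single-arm study of about 30 subjects, readers will look at the range as well as the mean, and the summary table alone would not reveal the substitution.

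The two secondary points are places where a programmer has to infer what was meant: which untimed Day 1 records the baseline sentence covers, and which numbered grade a missing severity receives.

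**Working it through.** **Inputs.** From the SAP: the threshold of 9 in the worked example (6.2) and about 30 subjects (4.1). Everything else below is assumed for illustration. The 9 is the SAP's generic example and not a limit for a named analyte.

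**1. Reproduce the SAP's figure.** 9 / 2 = 4.5, as the SAP states for `< 9`.

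**2. Compare the two signs.**
- For `< 9` and a non-negative quantity, the true value lies between 0 and 9, so the error of 4.5 is at most 4.5 in either direction.
- For `> 9`, the true value exceeds 9, so the error is more than 9 − 4.5 = 4.5, always downward, with no upper limit.

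**3. Effect on one visit's summary.** Take 29 values evenly spaced from 5.0 to 8.5 (sum 29 × 6.75 = 195.75) and one result of `> 9`.

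| Treatment of `> 9` | Minimum | Maximum | Mean |
|---|---|---|---|
| Set to the threshold, 9 | 5.0 | 9.0 | (195.75 + 9) / 30 = 6.825 |
| Halved, 4.5 | 4.5 | 8.5 | (195.75 + 4.5) / 30 = 6.675 |

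The highest subject becomes the lowest.

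**4. Effect on the mean for k such results in 30.** The shortfall against the threshold is 4.5k / 30: 0.15, 0.30 and 0.45 for k = 1, 2 and 3, or 1.7%, 3.3% and 5.0% of the threshold. The shortfall against the true mean is larger, because each true value is above 9.

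**5. Effect on change from baseline.** With baseline 8 and follow-up `> 9`, the true change is more than 9 − 8 = +1. The halved value gives 4.5 − 8 = −3.5. The sign reverses for any baseline between 4.5 and 9.

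**6. Secondary points, side by side.**
- *Baseline.* The first sentence of the SAP 6.3 definition admits only observations before dosing. The assessment-windows bullet in SAP 6.2 says that visit information from the CRF governs the outputs. SAP 6.6 lists Baseline and Day 1 post-dose as separate labels. Together these imply that the untimed rule is for pre-dose records, but the sentence itself does not say so.
- *Severity.* One phrase points to the top of the scale and the other gives a word instead of a number, while the tables use numbers. One subject with one ungraded event is 1 / 30 = 3.3% of the population, so that is the size of the ambiguity per such subject.

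**The case against.** The best defence of SAP 6.2 is that the bullet is permissive and that every illustration in it is a less-than result, so the authors probably had only those in mind. That is likely, and it explains the wording. It does not remove the problem, because the sentence names both signs and no visible text tells the programmer what else to do with a greater-than result.

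It is also fair that no analyte reportable with a greater-than sign is identified, that the laboratory panel is not visible in this copy, and that the original result stays in the listings. Parts of SAP section 6 are not visible either (the numbering passes from 6.4 to 6.6), so a clarification there cannot be excluded. These points stand and keep the matter minor.

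Three stronger readings are tempting, and the documents do not support them.

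- *The shift tables and normal/abnormal counts are also wrong.* SAP 17.2 bases normal and abnormal on a test-specific normal range and does not say that converted values feed these tables. SAP 6.2 describes conversion as a step before summary statistics.
- *An untimed post-dose vital sign or ECG can become baseline, with nothing to choose between it and a timed pre-dose record.* A reader might support this by contrast with the missing-time rule for adverse events, which applies where "it cannot be confirmed that onset was prior to the start of dose administration the AE will be reported as TEAE". But that rule decides whether an event is treatment-emergent, which is a different question. The pre-dose limit in the first sentence of the definition, the CRF visit rule and the separate post-dose label already identify such a record without a clock time. Protocol 6.3.9 also requires the pre-dose safety laboratory tests before Day 1 dosing.
- *A missing severity falls in no row of the tables, or must be counted as Grade 5.* The grade definitions are not visible here, so neither can be established. What remains is a mismatch between a word and a set of numbers.

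**Conclusion.** The conversion rule in SAP 6.2 is wrong as written for greater-than results, and the point is minor. Applied literally, it replaces a value above the threshold with half the threshold, an error of more than half the threshold per result. That can misstate the minimum, maximum, mean and direction of change in the laboratory summaries. In the illustration, one to three such results among 30 lower the mean by 0.15 to 0.45 relative to using the threshold; the extremes and individual changes are affected more visibly.

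This rests on the visible wording. The sizes use assumed data and would be zero if no laboratory result is reported with a greater-than sign. The consequence is confined to descriptive safety summaries: no efficacy result or sample size changes.

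The baseline sentence and the severity imputation are wording clarifications. The first makes explicit what the SAP already implies; the second resolves a small labelling conflict.

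**What to change.** - **SAP 6.2.** Limit halving to less-than results. State that greater-than results are set to the threshold itself, and footnote every table in which this is done. The threshold is a lower bound, so the footnote should say that the maximum and mean may be understated. Replace the optional wording with a definite rule.
- **SAP 6.3.** Add that the rule for an untimed Day 1 assessment applies only to records whose CRF label is Baseline or pre-dose.
- **Adverse event imputation text under SAP 6.4.** Name one CTCAE grade for a missing severity, consistent with protocol 6.3.2.1 and the tables in SAP 17.1, and footnote imputed events.

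The cost is about three sentences and the matching footnotes. No new data are needed.
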